4.1 Screening/Baseline Visit procedures

At clinic sites, recruitment procedures will be implemented either by a clinical coordinator who is a regular member of the clinic staff or a research staff member working under the supervision of a clinic staff member. For participants recruited via the AR-POWER network or Creaky Joints, a research staff member will implement recruitment procedures.

Potential participants will be interviewed to assess eligibility. Eligible participants will complete a telephone interview and a baseline questionnaire delivered via the Internet using Qualtrics and REDCap. The telephone interview will ask the participant knowledge questions about RA and will assess their health literacy via the standardized Newest Vital Signs instrument. The baseline questionnaire will include a list of DMARDS currently available in the US for the treatment of RA. Participants will be asked to indicate the ones that they are currently using.

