4.2 Intervention/Treatment procedures (by visits)

After participants complete the baseline questionnaire, they will be randomly assigned to one of four study groups: Other CMI without Gist Reasoning Training, Other CMI with Gist Reasoning Training, DrugFactsBox[®] without Gist Reasoning Training, and DrugFactsBox[®] with Gist Reasoning Training. Note that in most cases the “Other CMI” provided will be FDA approved Medication Guides. However, not all DMARDS are required to have a Medication Guide. In these cases, the investigators will provide CMI developed by the American Society of Health-System Pharmacists[®]. These materials are similar to the CMI that is given to patients in the United States when prescriptions are dispensed.

Participants will then be directed to a website that provides written prescription drug information (either Other CMI or DrugFactsBoxes[®], depending on group assignment) for the medications they are currently using. The website will allow participants to print a hard copy of the materials, if desired. The website will also allow them to access information about other DMARDS. For participants randomized to the gist training group (SMART Program), staff at the Center for BrainHealth at the University of Texas-Dallas will contact participants, either by email or by phone, to enroll them in the next SMART Program. The training program will be delivered in small groups of 5-6 individuals over a 1-month period. Each program will include 4 60-minute sessions delivered by research personnel certified to provide the program. Training will be presented via an online video conferencing platform, such as BlueJeans[®], that permits synchronous, audio and visual communication between trainers and participants. Participants only need a computer (desk, laptop, tablet) or mobile phone with internet access to participate.

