DMARD Usage will be assessed via the online questionnaires. Participants will be shown a checklist of 19 medications used to treat RA (abatacept, adalimumab, azathioprine, certolizumab pegol, cyclosporine, etanercept, golimumab, gold, hydroxychloroquine, infliximab, leflunomide, methotrexate pill, methotrexate shot, minocycline, rituximab, sulfasalazine, tocilizumab infusion, tocilizumab shot, and tofacitinib) and asked to check all of those that they are currently using. Participants will also be to check an option labeled *None of the above*. DMARD Usage will be scored as “0” if the participant reports using no DMARDS and “1” if the participant reports using one or more DMARDS.

Informed Decision-Making. Participants will be classified as meeting the criteria for informed decision making if they:

- (1) Answer at least 85% of the knowledge items correctly, score greater than 0 on the values scale indicating favorable attitudes concerning the use of medications to control disease activity, and are using a DMARD **OR**
- (2) Answer at least 85% of the knowledge items correctly, score 0 or less on the values scale indicating reluctance to use medications to control disease activity, and are not currently using a DMARD.

Individuals who fail to meet either set of criteria will be classified as not meeting the criteria for informed decision-making.

Proximal Secondary Outcomes: The investigators will assess five proximal secondary outcomes: Gist Reasoning Ability; Selective Learning; Information Seeking; and two specific types of knowledge, Verbatim Recall and Medication Self-Management Knowledge. These variables, which are described below, are considered proximal because the investigators conceptualize them as direct effects of the intervention.

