Verbatim Recall of information concerning potential medication benefits and harms will be assessed by medication-specific items developed specifically for this study. For each medication, the investigators will identify one potential benefit and one potential harm listed in the Drug Facts Box. Each question will ask participants about the probability of benefit/harm using a multiple-choice response format. To minimize response burden, participants will be asked these questions in relation to only one of their current RA medications. For participants taking more than one RA medication, the investigators will ask the items in relation to methotrexate, if methotrexate is being used. Otherwise, the investigators will ask the items in relation to the most commonly used biologic medication the participant is using or, in cases where the participant is not using any biologic medications, the investigators will ask the items in relation to a non-biologic medication. Correct responses will be summed across the benefit and harm items to yield a score ranging from 0 to 2. This measure will be administered, by telephone interview, only at the 6-week follow-up.

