For this study, the investigators will create a website that contains 16 Drug Facts Boxes for those medications most commonly used to treat RA in the United States (i.e., abatacept, adalimumab, certolizumab, etanercept, golimumab, hydroxychloroquine, infliximab, leflunomide, methotrexate pill, methotrexate shot, prednisone, rituximab, sulfasalazine, tocilizumab infusion, tocilizumab shot, and tofacitinib). A pill bottle icon for each of these medications will appear on the website landing page. When the icon for a medication is clicked, an overview of the medication will appear. The overview will include a section labeled *Bottom Line* which contains a narrative summary of potential medication benefits and harms, emphasizing bottom-line gist. The overview page will also provide links to other pages within the website that contain additional information about the medication. These links will be labeled: Trials, Side Effects, How to Use, Lifestyle Changes, and Interactions. The Trials page will provide quantitative information

concerning potential medication benefits and harms, mirroring the original DrugFactsBox[®] format.

Effects of the DrugFactsBox[®] format will be evaluated in comparison to other types of written CMI. All participants assigned to receive Other CMI will be given access to a website that contains CMI for the same 16 medications listed above. For medications that have an FDA-approved Medication Guide (i.e., abatacept, adalimumab, certolizumab, etanercept, golimumab, infliximab, rituximab, tocilizumab infusion, tocilizumab shot, and tofacitinib), the website will provide a link to the Medication Guide. For the remaining medications (i.e., hydroxychloroquine, leflunomide, methotrexate pill, methotrexate shot, prednisone, and sulfasalazine), the website will provide a link to CMI developed by the American Society of Health-System Pharmacists[®]. These materials are similar to the CMI that is given to patients in the United States when prescriptions are dispensed. The DrugFactsBox[®] website and the Other CMI website will both allow participants to print a hard copy of the materials, if desired.

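### DMARD use, which enters both routes to the primary outcome, is scored from a closed 19-entry list, and four listed drugs have no study material; both gaps are narrow and of unknown size, but cheap to close

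*Combined protocol and SAP*

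**What the plan says.** **DMARD use (Section 5.1).** "Participants will be shown a checklist of 19 medications used to treat RA". The only residual response described is this: "Participants will also be to check an option labeled" *None of the above*. Usage is scored 1 "if the participant reports using one or more DMARDS" and 0 otherwise. Section 4.1 describes the baseline version this way: "The baseline questionnaire will include a list of DMARDS currently available in the US for the treatment of RA". Section 4.5 (concomitant medication documentation) is marked not applicable.

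**Role in the primary outcome (Section 5.1).** Both routes require at least 85% of knowledge items correct. The first adds: "score greater than 0 on the values scale indicating favorable attitudes concerning the use of medications to control disease activity, and are using a DMARD". The second requires a values score of 0 or below and no current DMARD.

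**Study material.** Section 4.2 sends participants to a website with written information "for the medications they are currently using". Section 7 says the study website "contains 16 Drug Facts Boxes for those medications most commonly used to treat RA in the United States", and that the Other CMI website covers the same 16.

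**Medication-specific measures (Section 5.1).** On Verbatim Recall: "For each medication, the investigators will identify one potential benefit and one potential harm listed in the Drug Facts Box". Medication Self-Management Knowledge has 42 side-effect items and three scenario items; the scenario items are to come from the information supplied to participants. Both measures target one drug: methotrexate if used, otherwise a biologic, otherwise a non-biologic.

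**The concern.** The use code does more than add noise to the primary outcome. Among participants with adequate knowledge, it decides which side of the classification they fall on. A user of a DMARD outside the list has nothing to tick but *None of the above*, and nothing else described in the plan would reveal the omission.

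Three features make an incomplete list plausible: the study is expected to last 3 years, use is recorded at four time points with no described update of the list, and the synopsis admits inflammatory arthritis similar to RA while the checklist is of drugs used to treat RA.

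The second concern is a mismatch between lists. If a participant's target drug is on the checklist but on neither website, no information format was delivered for that drug in any arm, and part of the measurement has no stated source.

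**Working it through.** **1. What a wrong use code does.** Take a participant whose sole DMARD is unlisted, so that true use is 1 and recorded use is 0.

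| Knowledge | Values | True class | Recorded class |
|---|---|---|---|
| at least 85% | above 0 | informed | not informed |
| at least 85% | 0 or below | not informed | informed |
| below 85% | any | not informed | not informed |

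Anyone who also uses a listed DMARD is scored 1 and is unaffected.

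**2. The two drug lists (Sections 5.1 and 7).** The checklist has 19 entries and the websites 16. On the checklist only: azathioprine, cyclosporine, gold, minocycline. On the websites only: prednisone. Shared: 19 − 4 = 15, and 15 + 1 = 16.

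**3. The plan's own power figure (Section 6.4).** Inputs: 60% v 35%, two-sided alpha 0.05, 80% power, 15% attrition, 75 per arm.

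n = [1.960 √(2 p̄ q̄) + 0.842 √(p₁q₁ + p₂q₂)]² / d², with p̄ = 0.475 and d = 0.25

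= [1.960 × 0.7062 + 0.842 × 0.6837]² / 0.0625 = 61.4, so 62 per arm; 62 / 0.85 = 72.9, so 73, against the stated 75.

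Power = Φ{[d√n − 1.960 √(2 p̄ q̄)] / √(p₁q₁ + p₂q₂)}. With n = 75 × 0.85 = 63.75 this is Φ(0.895) = 81.5%. The stated figure therefore fits two single arms. For the factorial margin (two arms pooled against two, n = 127.5 a side) power is Φ(2.104) = 98.2%.

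**4. Dilution if the list stays closed.** The documents do not give the share m whose sole DMARD is unlisted; 1% to 10% is an assumed range. Assume the same m in every arm and that no miscoded participant is recorded as informed. Each rate then becomes p(1 − m). At m = 5%: 0.60 × 0.95 = 0.570 and 0.35 × 0.95 = 0.3325, so d = 0.2375.

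| m | Rates | Power, two single arms | Power, factorial margin |
|---|---|---|---|
| 0 | 60.0 v 35.0% | 81.5% | 98.2% |
| 1% | 59.4 v 34.7% | 80.7% | 98.1% |
| 2% | 58.8 v 34.3% | 79.9% | 97.9% |
| 5% | 57.0 v 33.3% | 77.5% | 97.2% |
| 10% | 54.0 v 31.5% | 73.4% | 95.7% |

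If instead 70% to 90% of affected participants hold favourable values, alike in all arms, some reluctant users are recorded as informed. At m = 5%, power is then about 78% to 79% for two single arms and 97.3% to 97.7% for the margin. These are crude two-proportion figures: they ignore the baseline covariate and do not address the interaction test for Hypothesis 3.

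In numbers of people, 1% to 5% of 300 is 3 to 15. Among the roughly 300 × 0.85 = 255 in the 6-month analysis it is about 3 to 13, before the knowledge condition is applied.

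**5. Who meets the website gap.** Under the target-drug order, one of the four uncovered drugs can be the target only for a participant on neither methotrexate nor a biologic. If such a participant also uses a covered non-biologic, the plan does not say which is chosen. Where an uncovered drug is the target, there is no Drug Facts Box from which to write the two Verbatim Recall items. For Medication Self-Management Knowledge, 3 of 45 items lose their source, and 42 remain scoreable.

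**The case against.** The strongest reply on the primary outcome is Section 4.1, which presents the baseline list as the DMARDs available in the US. No section names one outside it, and naming one would need outside knowledge. A reader might infer that the primary outcome is known to be misclassified, or that any use of an unlisted DMARD reverses it. The documents support neither. The code is wrong only if the unlisted drug is the sole DMARD, and the classification changes only with at least 85% knowledge. Nor do they suggest bias between arms, since every arm gets the same checklist. All of this stands and limits the size. It does not remove the gap: Section 4.1 speaks only of the baseline list and of RA.

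On the second part, restricting the websites to the commonest drugs is a stated scope choice. A reader might infer that the medication-specific measures cannot be scored for anyone using one of the four drugs. That is too strong, given the target-drug order and the 42 unaffected items. Verbatim Recall is measured only at 6 weeks and is not among the 18 secondary outcomes in Section 6.3, and neither measure enters the primary outcome. What stands against the plan is that it has no rule for an uncovered target drug, and that the Section 4.2 description does not fit users of those drugs.

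A practical objection also has force. Table 1 already reports baseline alphas and one 6-week alpha, which suggests that data collection had begun. A field added midway would make coding differ between time points, and baseline Informed Decision-Making is a model covariate.

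**Conclusion.** The point holds as two limited gaps.

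First, the scoring rule as written would code a participant whose sole DMARD is unlisted as a non-user, and would reverse the primary classification where knowledge is adequate. The number affected cannot be established from the documents. On the assumed 1% to 5%, with no miscoded participant recorded as informed, the cost is about 1 to 4 points of power for two single arms and 1 point or less for the factorial margin that Hypotheses 1 and 2 use. It is mainly dilution.

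Second, the list mismatch is exact: four checklist drugs have no study material and one website drug is not on the checklist. Its consequence is confined to participants on neither methotrexate nor a biologic whose target drug is one of the four. It touches one of the 18 secondary outcomes in part, and one further measure outside those 18.

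The change is worth making because it is cheap and because an unrecorded DMARD cannot be recovered from the data described.

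**What to change.** **Checklist.** Add 'Other RA medication (please specify)' at every time point. An existing investigator blinded to assignment codes each entry as DMARD or not, and DMARD Usage is 1 if any listed or coded drug is a DMARD. If collection has already begun, report the number ticking *None of the above* by arm and time point, as an upper limit on the number miscoded, and state how earlier assessments are coded.

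**Medication-specific measures.** At each assessment, choose the target drug from the 15 that are on both the checklist and the websites; this also settles prednisone. State how to choose among several covered non-biologics. Treat participants using none of the 15 as not assessable on these two measures. Restricting to users of a covered drug at baseline would not be enough alone, because a participant can switch or stop before 6 weeks or 6 months. That subset is fixed before randomisation, however, so use it for a sensitivity analysis.

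**Section 4.2.** Say that the information covers current medications that are among the 16.

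**Cost.** One survey field, a little blinded coding and a few sentences in Sections 4.2, 5.1 and 6.3. The planned sample size is unchanged. A few participants leave the two medication-specific measures.

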Gist Reasoning Ability, also referred to as integrated reasoning, will be assessed by the Test of Strategic Learning (TOSL). The TOSL was developed by Chapman and colleagues to systematically quantify participants’ capacity to synthesize and interpret high-level meaning from lengthy multi-faceted textual information.^{59,60} The TOSL consists of four text passages of similar length and complexity. At each data collection point, participants will read one of the text passages presented via an online learning platform. (The texts, as well as their order of presentation, will be randomized at each assessment so that participants will not see the same text twice.) Participants will not be allowed to return to the passage once they finished reading. After reading the passage,

participants will be asked to provide a synthesized, condensed version of the text in their own words, conveying primarily high-level ideas of substance rather than specific details. They will be given five minutes to complete this task. Participants will then be asked to generate as many interpretations (i.e., lessons learned) as possible that could be derived from the passage. They will be given three minutes to complete this task.

Responses will be scored using a manualized, objective scoring system by a trained and experienced rater, based at the Center for BrainHealth, who is blinded to participants' group assignment and time point of testing. Two separate scores will be derived from participant responses: number of abstracted ideas (Complex Abstraction) and a weighted index reflecting the quantity and quality of high-level interpretations (Lesson Quality). High-level interpretations will be judged against a rubric based on the specific content of each passage.

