Selective Learning is defined as the ability to optimize processing of incoming information by controlling working memory to try to remember high value information while inhibiting low value information.⁶¹ To assess this ability, the Visual Selective Learning (VSL) task will be administered as part of each telephone interview by showing participants 3 lists of 16 words via a PowerPoint presentation imbedded in a YouTube video. Each word will appear on a separate screen for 1 second. Half of the words will be in uppercase and half will be in lowercase. In some trials, participants will be instructed that uppercase words are valued at 10 points and lowercase words at 1 point; in other trials, the point value was the opposite. Participants will be told to remember as many words as they could, but that their goal is to earn as many points as possible. Different word lists will be used at each time point and the lists will be balanced across participants over the course of the study using procedures parallel to those for the TOSL. At each time point, scores will be summed across the three lists, yielding a composite score with a possible range from 0 to 264.

Information Seeking will be assessed using two behavioral measures incorporated into the design of the study. First, the investigators will create a website that provides easy access to information about RA, treatment options, and self-management strategies. The investigators will refer to this website at the RA Self-Management Website. Participants will be emailed a link to this website immediately after completion of 6-week follow-up data collection. The investigators will use Google analytics to track whether participants accessed the website and the specific website pages viewed. Second, immediately after completion of 6-week follow-up data collection, the investigators will email all participants an invitation to take part in BetterChoices, BetterHealth®, an online chronic illness self-management program, free of charge. The investigators will track whether or not participants enroll in the class, the number of class sessions attended, and whether or not participants complete the class.

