The investigators will assess objective health literacy using the Newest Vital Sign (NVS).⁸⁴ This measure asks participants to look at the nutrition label from a pint container of ice cream. While looking at the label, participants are asked six questions (e.g., “If you ate the entire container, how many calories would you eat?”). Correct answers will be summed and then transformed to a 100 point scale, reflecting the percentage of questions answered correctly. In previous research, this measure has demonstrated internal consistency (i.e., Cronbach alpha =0.76) and construct validity (strong correlations with TOFHLA). Because the investigators will administer this measure twice in the current study, the investigators were concerned that memory effects would artificially inflate scores at the second assessment. Therefore, the investigators created a second version of the NVS based on the same ice cream container label, but with slightly modified questions. Participants will complete one version at baseline, determined randomly and balanced across participants, and the other version at the 6-month follow-up.

Medication Adherence will be assessed by a single question that asks: “All things considered, how much of the time do you use your RA medications EXACTLY as directed?” Responses will be recorded on a 100-point visual analog scale with endpoints labeled “None of the Time” and “All of the time”.

Other Participant Characteristics: For descriptive purposes, The investigators will also collect the following socio-demographic information from study participants: age; gender (male, female); race (African-American, American Indian or Alaskan Native, Asian, Native Hawaiian, or Other Pacific Islander, White, Other); ethnicity (Hispanic, non-Hispanic); education (less than high school, high school diploma only, some college or technical school, college degree); marital status (never married, married, widowed, divorced, separated); and ability to afford medications (no trouble, a little trouble, a lot of trouble).

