Fatigue	B, 6M	Self-Administered Questionnaire	T-Score: Mean =50, SD=10 in reference population	NA
Disease Activity	B, 6W, 3M, 6M	Self-Administered Questionnaire	0 to 10	0.81
Global Health Status	B, 6M	Self-Administered Questionnaire	1 to 4	NA
Subjective Health Literacy	B, 6M	Self-Administered Questionnaire	0 to 4	0.80
Objective Health Literacy	B, 6M	Telephone Interview	0 to 100	Version A: 0.60 Version B: 0.49
Medication Adherence	B, 6M	Self-Administered Questionnaire	0 to 100	NA

†A separate online, self-administered questionnaire was used to assess Gist Reasoning Ability. It was completed before participants did the questionnaire assessing other study measures.

††This variable was only assessed at the 6-week follow-up. Therefore, the alpha reported is for that time point.

NOTE: For all variables except Global Health Status, higher values reflect higher levels of the attribute measured. For Global Health Status, higher values reflect poorer health status.

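### The Objective Health Literacy model omits the randomised NVS version, which costs some precision if the two versions differ in difficulty

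*Combined protocol and SAP*

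**What the plan says.** Section 5.1 explains that the NVS is given twice and that the investigators were worried about memory effects. They therefore "created a second version of the NVS based on the same ice cream container label, but with slightly modified questions". On allocation it says: "Participants will complete one version at baseline, determined randomly and balanced across participants", "and the other version at the 6-month follow-up". No equating study, score conversion or comparison of mean difficulty is described. Table 1 in the appendix gives baseline internal consistency by version ("Version A: 0.60 Version B: 0.49") but no means.

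Section 6.3 specifies the primary model: baseline status, a SMART indicator and a DrugFactsBox indicator, with two-way interactions in separate models. It carries this approach over to 18 secondary outcomes, one of which is Objective Health Literacy. No term for version, passage or word list appears in any model.

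Two other instruments also rotate forms. For the Test of Strategic Learning (TOSL), which yields Complex Abstraction and Lesson Quality, section 5.1 says: "The TOSL consists of four text passages of similar length and complexity". The texts, "as well as their order of presentation, will be randomized at each assessment". For Selective Learning: "Different word lists will be used at each time point and the lists will be balanced across participants".

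**The concern.** Version is a known, randomised source of variation in the NVS score. Everyone takes both versions, half in each order, so a difficulty gap acts in two places. It widens the spread of the 6-month score. It also moves the baseline score in the opposite direction, which weakens the correlation that baseline adjustment depends on. The planned model leaves both effects in the residual. What is at stake is the width of the confidence interval and the power for one secondary outcome, which must also pass a Hochberg adjustment across 18 endpoints.

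**Working it through.** **Plan's own figure.** The documents give no variance, correlation or power for Objective Health Literacy. Section 6.4 concerns the primary outcome only. It is used here just for the number analysed: 300 × (1 − 0.15) = 255.

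**Inputs from the documents.** Two versions, randomised and balanced at baseline, then crossed over (5.1). Model terms are baseline and two intervention indicators (6.3). I read the baseline term as the baseline value of the outcome being analysed; section 6.3 spells it out only for the primary outcome.

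**Assumptions.** A difficulty gap d between versions of 0.1 to 0.5 SD, and a baseline-to-6-month correlation ρ of 0.4 to 0.7. Neither is in the documents.

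**Formulae.** Take within-version variance as 1 and let a = d²/4. The version shifts a participant by +d/2 at one visit and −d/2 at the other.
- With a version term, residual variance = 1 − ρ².
- Without it, each score has variance 1 + a and their covariance is ρ − a, so residual variance = (1 + a) − (ρ − a)²/(1 + a).

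**Worked case, d = 0.2, ρ = 0.5.** a = 0.01. With the term: 0.75. Without: 1.01 − 0.49²/1.01 = 0.7723. Ratio 0.7723/0.75 = 1.030.

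**Worked case, d = 0.5, ρ = 0.5.** a = 0.0625. Without the term: 1.0625 − 0.4375²/1.0625 = 0.8824. Ratio 0.8824/0.75 = 1.176.

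Variance inflation from omitting version:

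| Gap (SD) | ρ = 0.4 | ρ = 0.5 | ρ = 0.6 | ρ = 0.7 |
|---|---|---|---|---|
| 0 | 0% | 0% | 0% | 0% |
| 0.1 | 0.6% | 0.7% | 1.0% | 1.4% |
| 0.2 | 2.3% | 3.0% | 4.0% | 5.6% |
| 0.3 | 5.1% | 6.6% | 8.8% | 12.5% |
| 0.5 | 13.7% | 17.6% | 23.5% | 33.3% |

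For an effect that would have 80% power with the version term, power without it at ρ = 0.5 is 79.7%, 78.8%, 77.4% and 73.3% for the four non-zero gaps.

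**Validity check.** Trials were simulated with 255 participants, 6,000 per scenario, ρ of 0.5 and 0.6, and gaps of 0.2, 0.3 and 0.5 SD. Leaving version out gave a mean estimate under the null within −0.002 to +0.003 SD and a type I error of 4.7% to 5.2%. At ρ = 0.5, power without and with the term was 78.2% and 79.4% (gap 0.2), 77.6% and 80.2% (0.3), and 72.7% and 78.9% (0.5), in line with the formula.

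**Cost of adjusting.** One extra term costs about 1/255 = 0.4% of variance if the versions are equal.

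**The same question for the TOSL.** Adjusting for the baseline and the 6-month passage takes 3 + 3 = 6 indicators, costing about 6/255 = 2.4% if the passages are equal. With four passages drawn without replacement and SD of difficulty s, the passage effects at the two visits have covariance −s²/3. At s = 0.10 and ρ = 0.5, residual variance without the terms is 1.01 − (0.5 − 0.0033)²/1.01 = 0.7658, and 0.7658/0.75 = 1.021. Net of the six terms, 1.021/1.024 = 0.997, which is roughly break-even.

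**The case against.** The strongest reply is that the plan contains no error. Randomising and balancing the forms is itself the control for form difficulty, and the planned analysis is valid without a version term. The second NVS version uses the same label with lightly altered questions, so a gap of 0.1 to 0.2 SD is more plausible than 0.5 SD, and at ρ = 0.5 that is a loss of 1% to 3%. All of this stands, and it is why the point is a small improvement and not a defect.

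Four stronger readings are tempting, and the documents do not support them.

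- A reader might infer bias, because balance is stated across participants and not within arm. Version is randomised independently of arm, so any chance imbalance is already part of the standard error. It is the same loss of precision, not a second harm.
- A reader might take "Version A: 0.60 Version B: 0.49" as proof that one version is harder. Alpha measures internal consistency, not mean difficulty. The difference is also compatible with chance: assuming 150 participants per version, a Feldt-type ratio is (1 − 0.49)/(1 − 0.60) = 1.275, p about 0.14.
- A reader might extend the point with equal force to Complex Abstraction, Lesson Quality and Selective Learning. The TOSL passages are described as comparable, and the scoring adapts to the text: "High-level interpretations will be judged against a rubric based on the specific content of each passage". That is not equating, but it counts as mitigation. The Selective Learning score sums three lists, which averages out list difficulty. The number of list sets is not stated, so no loss can be calculated for it.
- A reader might suppose that adding form terms everywhere is free. It is nearly so for the single NVS term, but six passage terms lose about 2% if the passages are equal.

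**Conclusion.** The point holds as a minor gain in efficiency for one secondary outcome. The NVS is the clear case: the second version was made for this study, no equating is described, the versions cross over between visits, and one term captures the whole effect. The size depends on an unknown gap. At ρ = 0.5 the inflation runs from zero to about 18% for gaps up to 0.5 SD; at ρ = 0.7 it is about 6% for a gap of 0.2 SD and 33% for 0.5 SD. It also depends on the model adjusting for the baseline NVS score. Without the version term the analysis remains unbiased, with type I error at its nominal level. For the TOSL and Selective Learning outcomes the documents do not establish a worthwhile gain, so form terms there are a matter of choice.

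**What to change.** In section 6.3, state that the Objective Health Literacy model will include one indicator for NVS version order (A then B, or B then A), and fix this before outcomes are examined by arm. One indicator is enough, because the baseline version determines the 6-month version. Report baseline mean and SD by version, so that readers can see the gap. Table 1 already gives alpha by version, so the version each participant took at baseline must be identifiable.

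The cost is one sentence, one degree of freedom and about 0.4% of variance if the versions are equally hard.

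For Complex Abstraction, Lesson Quality and Selective Learning, passage or list terms may be added if the sponsor wishes. The choice should be prespecified, knowing that six indicators pay off only if the SD of form difficulty exceeds about 0.1.
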